6.10.1 Data Submission

If the subject undergoes a non-study MRI scan at any time during the study, complete and submit the appropriate forms to St. Jude Medical.

Upload device session records, if applicable and available, through the EDC study site portal. Device session records may also be sent to St. Jude Medical CRMD, Sylmar, CA.

It is recommended that the following forms, device printouts and measurements be maintained at the site.

- MRI Hazard Checklist
- FastPath Summary
- Test Results with Large Freezes, Include Battery & Leads
- Wrap-up Overview with full parameters

6.11 Description of Activities performed by Sponsor Representatives

Trained sponsor personnel may perform certain activities to ensure compliance to the clinical investigational plan and may provide technical expertise. Sponsor field clinical engineers may perform the following activities:

- Interrogation of and testing the implanted ICD system at any study visit (scheduled or unscheduled): capture, sense, pacing and HVLI measurements,
- Verifying MRI scan parameters on the programmer at the MRI Scan Visit or Non-Study MRI visit,
- Programming of the ICD per protocol, and/or as directed by the investigator/designee.

While sponsor representatives may perform these activities, the principal investigator remains responsible for ensuring all study data is collected as required per protocol. Deviations resulting from failure to comply with protocol requirements will be reported through completion of a Deviation CRF.

Clinical Investigational Plan

6.12 Subject study completion

The minimum duration of each subject's participation is approximately one month from the MRI scan (1 Month Post Scan visit). The VT/VF data collection effort will continue until a minimum of 25 subjects with at least one VT/VF episode (spontaneous or induced) has been adjudicated by the Ventricular Arrhythmia Events Committee. SJM will notify sites when the VT/VF data collection effort has ended. When the subject's participation in the clinical study has been completed the subject will return to standard medical care as per physician's recommendation.

6.13 Any Known or Foreseeable Factors that May Compromise the Outcome of the Clinical Study or the Interpretation of the Results

All foreseeable factors that may compromise the outcome have been taken into account by the clinical study design and well defined subject selection criteria.

6.14 Description of the Methods that will be used to Address Potentially Confounding Factors in the Clinical Study Design

The efficacy endpoints are change in bipolar ventricular capture and sensing threshold from pre-MRI scan to 1 Month Post Scan for the RV high voltage lead implanted with the Ellipse VR ICD. Each subject therefore acts as his/her own control. Therefore, there is no concern for confounding factors for the efficacy endpoint.

6.15 Criteria and Procedures for Subject Withdrawal or Screen Failure

Subjects must be informed about their right to withdraw from the study at any time and for any reason without sanction, penalty or loss of benefits to which the subject is otherwise entitled and withdrawal from the study will not jeopardize their future medical care or relationship with the investigator. Subjects will be asked to specify the reason for the termination, but have the right not to answer.

The investigator may decide to withdraw a subject from the study at any time with reasonable rationale. The subject's future care will not be influenced by a decision, voluntary or otherwise, to withdraw from the study. All reasonable efforts should be made to retain the subject in the clinical study until completion of the study.

Reasons for subject's withdrawal include, but are not limited to:

- Subject refuses to continue participating in the study
- Subject is deceased (cause must be documented)
- Subject's non-compliance

Clinical Investigational Plan

- Subject's participation is terminated by the PI or investigator, although the subject consented, since participation is no longer medically appropriate
- Subject is 'lost to follow up': Subject does not adhere to the scheduled follow up visits but has not explicitly requested to be withdrawn from the clinical study. (This does not apply to missed visits). Site personnel should at all times make all reasonable efforts to locate and communicate with the subject in order to achieve subject compliance to the scheduled follow up visits:
 1. A subject will be considered 'Lost to Follow Up' after a minimum of 2 phone calls of a physician or delegate at the investigational site to the subject or contact. These 2 phone calls need to be documented in the subject's hospital records.
 2. If these attempts are unsuccessful, a certified letter should be sent to the subject's last known address or general practitioner (GP) and a copy of this letter should be maintained in the subject's hospital records.

If a subject withdraws from the clinical study, the site will record the subject's reasons for withdrawal, on a Withdrawal CRF.

When subject withdrawal from the clinical study is due to an adverse event the subject will be followed until resolution of that adverse event or determination that the subject's condition is stable. The status of the subject's condition should be documented at the time of withdrawal.

Screening Failure: A subject may also become a screen failure based if the subject's participation ended prior to enrollment in the study. Refer to section 6.5.2 Situations where the subject does not meet enrollment criteria and 6.8.1 Revisions Before the MRI Scan. Complete a Screening Failure CRF for screen failure subjects and note that the subject is a screen failure.

7.0 Compliance to the CIP

7.1 Statements of Compliance

The study will be performed in accordance with the most current versions of the World Medical Association (WMA) Declaration of Helsinki, ISO14155 and any regional and/or national regulations and will be compliant to this International Standard and any regional and national regulations, as appropriate.

The investigator will not start enrolling subjects or requesting informed consent from any subject prior to obtaining IRB/EC approval and Competent Authority approval, if applicable, and authorization from the sponsor in writing for the study.

Clinical Investigational Plan

In case additional requirements are imposed by the IRB/EC or Competent Authority, those requirements will be followed, if appropriate. If any action is taken by an IRB/EC, and regulatory requirements with respect to the study, that information will be forwarded to St. Jude Medical.

As sponsor, St. Jude Medical has taken up general liability insurance in accordance with the requirements of the applicable local laws. Appropriate country representative will be utilized to understand the requirements for the type of insurance that will be provided for subjects, such information will be incorporated into the informed consent, as applicable

If required, additional subject coverage or a study specific insurance will be provided by the Sponsor as well.

7.2 Adherence to the Clinical Investigation Plan (Protocol Deviations)

A deviation is defined as an event where the clinical investigator, site personnel, sponsor or sponsor representative did not conduct the clinical study according to the Clinical Investigational Plan, IRB/EC requirements or the Investigator Agreement. The investigator is not allowed to deviate from the CIP, except as specified under emergency circumstances.

In some cases, failure to comply with the CIP may be considered failure to protect the rights, safety and well-being of subjects, since the non-compliance exposes subjects to unreasonable risks. For example, failure to adhere to the inclusion/exclusion criteria: these criteria are specifically defined by the Sponsor to exclude subjects for whom the device is not beneficial and the use involves unreasonable risks. This may be considered failure to protect the rights, safety and well-being of the enrolled subject. Similarly, failure to perform safety assessments intended to detect adverse events may be considered failure to protect the rights, safety and well-being of the enrolled subject. Investigators should seek minimization of such risks by adhering to the CIP.

Simultaneously, in the event that adhering to the CIP exposes the subject to unreasonable risks, the investigator is also required to protect the rights, safety and well-being of the subject by intentionally deviating from the requirements of the CIP, so that subjects are not exposed to unreasonable risks.

It is the responsibility of the investigator to provide adequate medical care to a subject enrolled in a study.

Regulations require that the PI maintain accurate, complete, and current records, including documents showing the date of and reason for every deviation from the Clinical Investigational Plan. Relevant information for each deviation will be documented on a Deviation Case Report Form. The site will submit the CRF to St. Jude Medical.

Clinical Investigational Plan

Regulations require Investigators obtain approval from St. Jude Medical and the IRB/EC [as required] before initiating changes in or deviations from the protocol, except when necessary to protect the life or physical well-being of a subject in an emergency. Under emergency circumstances, deviations from the CIP to protect the rights, safety and well-being of human subjects may proceed without prior approval of the sponsor and the EC. Such deviations shall be documented and reported to the sponsor and the EC as soon as possible, but no later than 5 working days.

Prior approval must be requested when the PI anticipates, contemplates, or makes a conscious decision to depart from the CIP, except when unforeseen circumstances are beyond the investigator's control (e.g. a subject who fails to attend a scheduled follow-up visit, a subject is too ill to perform a CIP-required test, etc.). All deviations, including those beyond the investigator's control, must be reported on a CRF.

To obtain approval, the Principal Investigator may call or email and discuss the potential deviation with St. Jude Medical or designee prior to initiating any changes.

All deviations must be reported to appropriate regulatory authorities in specified timelines (if appropriate).

Investigator will notify St. Jude Medical and the reviewing IRB/EC within 5 working days of:

- Any deviation to protect the life or physical well-being of a subject in an emergency
- Any failure to obtain informed consent

Investigators or the designee must notify St. Jude Medical, Inc. as soon as possible and complete the Deviation CRF.

The Investigator is required to adhere to local regulatory requirements for reporting deviations to IRB/EC.

7.3 Repeated and Serious Non-compliance

In the event of repeated non-compliance or a one-time serious non-compliance, as determined by the Sponsor, a Clinical Research Associate or clinical representative will attempt to secure compliance by one or more of the following actions:

- Visiting the investigator
- Contacting the investigator by telephone
- Contacting the investigator in writing

Clinical Investigational Plan

- Retraining of the investigator

If an investigator is found to be repeatedly non-compliant with the signed agreement, the CIP or any other conditions of the clinical study, the Sponsor will either secure compliance or, at its sole discretion, terminate the investigator's participation in the clinical study.

8.0 Adverse Device Effect

8.1 Definitions

8.1.1 Medical Device

Any instrument, apparatus, implement, machine, appliance, implant, software, material or other similar or related article

(a) Intended by the manufacturer to be used, alone or in combination, for human beings for one or more of the specific purpose(s) of

- Diagnosis, prevention, monitoring, treatments or alleviation of disease,
- Diagnosis, monitoring, treatment, alleviation of, or compensation for, an injury,
- Investigation, replacement, modification, or support of the anatomy or of a physiological process,
- Supporting or sustaining life,
- Control of conception,
- Disinfection of medical devices and

(b) Which does not achieve its primary intended action in or on the human body by pharmacological, immunological or metabolic means, but which may be assisted in its intended function by such means

8.1.2 Adverse Device Effect (ADE)

An adverse device effect is an adverse event related to the use of an investigational medical device.

This definition includes adverse events resulting from insufficient or inadequate instructions for use, deployment, implantation, installation, or operation, or any malfunction of the investigational medical device.

This definition includes any event resulting from the use, error, or from intentional misuse of the investigational medical device.

Clinical Investigational Plan

8.1.3 Serious Adverse Device Effect (SADE)

Adverse device effect that has resulted in any of the consequences characteristic of a serious adverse event:

- Death
- A serious deterioration in the health of the subject, that either resulted in:
 - A life-threatening illness or injury OR
 - A permanent impairment to a body structure or a body function OR
 - An in-patient or prolonged hospitalization OR
 - A medical or surgical intervention to prevent life-threatening illness or injury or permanent impairment to a body structure or a body
- Fetal distress, fetal death or a congenital abnormality or birth defect

A planned hospitalization for a pre-existing condition, or a procedure required by the CIP is not considered a serious adverse event.

8.1.3.1 Unanticipated Adverse Device Effect (UADE)

As defined in 21 CFR §812.3, unanticipated adverse device effects (UADE) are defined as any serious adverse effect on health or safety or any life-threatening problem or death caused by, or associated with, a device, if that effect, problem, or death was not previously identified in nature, severity, or degree of incidence in the clinical investigational plan or application (including a supplementary plan or application), or any other unanticipated serious problem associated with a device that relates to the rights, safety, or welfare of subjects.

If an unanticipated adverse device effect occurs, the investigator must notify St. Jude Medical and the IRB/MEC immediately, but no later than 10 working days of the investigator's knowledge of the event, as required by 21 CFR §812.150. St. Jude Medical will take any steps necessary to investigate the event, and will be responsible for notifying FDA and all other participating IRBs/MECs and investigators.

8.1.3.2 Unanticipated Serious Adverse Device Effect (USADE)

A serious adverse device effect which by its nature, incidence, severity or outcome has not been identified in the current version of the risk analysis report.

8.1.4 Reporting of MRI Scan-Related Adverse Device Effects

An ADE or SADE related to the following should be reported as soon as possible, but no later than 10 working days, to St. Jude Medical: clotting, pulmonary embolism, or

Clinical Investigational Plan

heating of the device pocket during the MRI scan. These events are likely to be associated with symptoms occurring during or immediately following the MRI scan and may manifest as chest pain, shortness of breath, or changes in vital signs during or immediately following the MRI scan. To ensure all ADEs or SADEs related to or caused by the MRI scan are appropriately captured, follow the instructions in section 6.5.2.2 above.

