Study Visit		Visit Window	Study Procedures and Data Collection
1 Month Post MRI Scan Visit		30 days after MRI scan (- 7/+14 days)	
 Interrogate device Obtain in-clinic Durata or Optisure lead measurements: bipolar capture, sense, pacing and HVLI impedances^{1,2} Evaluate subject for ADE, SADE, UADE (for US sites) or USADE (for OUS sites) events and submit an AE CRF (as applicable). Report deviations, death, withdrawal and out of service as applicable Upload device session records through the EDC study site portal
Sub study induction testing		Can occur any time after the MRI scan visit (Suggest that testing occurs within 30 days after MRI scan visit: - 7/+14 days)	
 Conduct induction therapy testing (e.g. DC Fibber method) Evaluate subject for ADE, SADE, UADE (for US sites), USADE (for OUS sites) events and submit an AE CRF (as applicable). Report deviations, death, withdrawal and out of service as applicable Upload device session records through the EDC study site portal
Review of spontaneous VT/VF episodes (non-sub study subjects)	Subjects on Merlin.net	Capture events as they occur any time after the 1 month post MRI scan visit	
 Merlin.net records will be reviewed by SJM for spontaneous VT/VF Review of records will end upon notification from SJM
	Subjects not on Merlin.net	Every 3 months post baseline ± 30 days	
 Non-Merlin.net subjects: Follow up by phone with subject and screen medical records for VT/VF since last visit. Obtain the device data related to that VT/VF episode. Follow up phone calls will end upon notification from SJM.

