
 • Lead electrode heating and tissue damage resulting in loss of sensing or capture or both • Lead heating resulting in thrombus formation or embolism • Device heating resulting in tissue damage in the implant pocket or subject discomfort or both • Induced currents on leads resulting in continuous capture, VT/VF, hemodynamic collapse, or all three • Damage to the device or leads causing: 
 a. the system to fail to detect or treat irregular heartbeats b. the system to treat the subject’s condition incorrectly • Damage to the functionality or mechanical integrity of the device resulting in the inability of the device to communicate with the programmer • Movement or vibration of the device or leads • Lead dislodgment • Competitive pacing and potential for VT/VF induction due to ambulatory asynchronous pacing in MRI mode • Pulmonary Embolism 	
These risks are mitigated through the selection of investigators who are qualified by training and/or experience to evaluate and treat subjects implanted with an ICD system.
 
In addition, study investigators will be trained on the study protocol to ensure the proper procedures are followed to assure subject safety during the study MRI scan. This includes continuous monitoring of the subject using pulse oximetry, ECG and verbal communication during the scan.
 
Advanced Cardiac Life Support (ACLS) procedures will be in place to address situations where a life threatening arrhythmia and/or hemodynamic collapse occurs. The programmer will be used outside the American College of Radiology (ACR) defined Zone 4 magnet room. If the subject’s hemodynamic function is compromised during the MRI scan, the MRI scan will be stopped, and proper measures will be taken to restore the subject’s hemodynamic function.

Potential ICD Related Events	

 • Refer to the Ellipse user’s manual for a full list of potential adverse events 	
The Ellipse VR ICD is a market-released ICD. The adverse events associated with this ICD are the same as those associated with other market-released ICDs.
 
These risks are mitigated through the

Clinical Investigational Plan

Event	Mitigation
	selection of investigators who are qualified by training and/or experience to evaluate and treat subjects implanted with an ICD.
Potential Lead Related Events	

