4.4 Endpoints

4.4.1 Primary Safety Endpoint

Safety for the Ellipse VR ICD involving the Durata and Optisure leads will be evaluated in terms of:

- Freedom from MRI scan-related complications for the Ellipse VR ICD involving Durata or Optisure (RV) lead from MRI scan to 1 month post-MRI scan testing is greater than 90%

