6.5.2.2 Post-Scan Testing

Device Assessment and Programming

Following the MRI Scan, remove the subject from the MRI bore. Interrogate the ICD. Disable the MRI Settings. **Note: MRI settings must be disabled to ensure that tachyarrhythmia therapy is turned back on.** Obtain the following for the Durata or Optisure lead:

- In-clinic bipolar capture threshold at a pulse width of 0.5 ms. Either the manual decrement or automatic (in-clinic, programmer-based) method may be used to obtain the capture threshold.
- In-clinic bipolar sensing amplitude. Either the incremental or the automatic (in-clinic, programmer based) method may be used to obtain the sensing threshold.
- In clinic bipolar lead impedance
- In-clinic HVLI impedance

NOTE: RV capture thresholds are not required to be obtained if a high ventricular rate is present. If available, sites should use the automatically obtained pacing capture threshold from the most recent archival data as a substitute for the in clinic capture threshold. RV sensing measurements are not required if the subject's intrinsic rate is established to be ≤ 30 beats per minute.

Reporting of MRI Scan-Related Adverse Device Effects

An ADE or SADE related to the following should be reported as soon as possible, but no later than 10 working days, to St. Jude Medical: clotting, pulmonary embolism, or heating of the device pocket during the MRI scan. These events are likely to be associated with symptoms occurring during or immediately following the MRI scan and may manifest as chest pain, shortness of breath, or changes in vital signs during or immediately following the MRI scan.

To ensure all ADEs or SADEs related to or caused by the MRI scan are appropriately captured, before starting the scan, verbally instruct the subject to report symptoms of chest pain, shortness of breath or pocket discomfort that he/she experiences while being scanned or immediately after exiting the scanner. Note changes in vital signs such as changes in heart rate, room air blood oxygen saturation, and/or respiration rate that occur during the MRI scan that may suggest an ADE or SADE has occurred due to clotting, pulmonary embolus or related to lead tip or device pocket heating.

Clinical Investigational Plan

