12.1.1 Primary Safety endpoint

The primary safety endpoint #1 is: Freedom from MRI scan-related complications related to the Ellipse VR ICD involving Durata or Optisure (RV) lead from MRI scan to 1 month post MRI scan testing.

Hypothesis

The hypothesis is formally expressed as:

$$H_0: p_S \leq 90\%$$

$$H_a: p_S > 90\%$$

where p_S is the freedom from MRI scan-related complications(s) for the Durata or Optisure RV lead from MRI scan to 1 month after the MRI scan.

Analysis

The primary analysis will be conducted on subjects who meet all of the following criteria:

- Implanted with St. Jude Medical Durata or Optisure (RV) Lead
- Sign informed consent
- Meet the MRI Conditions of Use
- Undergo a Study MRI scan
- Have 1 month post-MRI scan visit or have MRI-scan related complication(s) for the Ellipse VR ICD involving Durata or Optisure RV lead before the 1 month post MRI visit

Clinical Investigational Plan

The hypothesis will be tested at the 2.5% significance level. The null hypothesis will be rejected if the 97.5% lower confidence bound for p_S is greater than 90%. The 97.5% lower confidence bound will be calculated by the exact (Clopper-Pearson) method for binomial probabilities.

12.1.2 Primary Efficacy Endpoint #1 (Change in Capture Threshold for Durata and Optisure (RV) Leads)

The primary efficacy endpoint #1 is the proportion of Durata or Optisure (RV) leads implanted with the Ellipse VR ICD with capture threshold increase of $\leq 0.5V$ at 0.5ms from pre-MRI scan to 1 month post-MRI scan testing.

Hypothesis

Success is defined as ventricular capture threshold increase of $\leq 0.5V$ at 0.5ms for the Durata or Optisure (RV) lead from pre-MRI scan testing to 1 month post-MRI scan.

The hypothesis is formally expressed as:

$$H_0: p_{E1} \leq 90\%$$

$$H_a: p_{E1} > 90\%$$

where p_{E1} is the probability of success.

Analysis

The primary analysis will be conducted on subjects who meet all of the following criteria:

- Implanted with the Durata or Optisure RV lead and Ellipse VR ICD
- Sign Informed consent
- Meet the MRI Conditions of Use
- Undergo a Study MRI scan
- Have MRI visit data for right ventricular capture threshold
- Have 1 month post-MRI scan visit data for RV capture threshold
- Have not undergone any VR ICD lead repositioning or replacement since the MRI scan up to 1 month post-MRI scan

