12.2 Sample size

12.2.1 Sample size for primary safety endpoint

In the St. Jude Medical Accent MRI pacemaker IDE study, the results of which were submitted in PMA 60067410/A, and another manufacturer's study involving an MRI conditional pacemaker, the complication-free rate was observed to be 100%.^{16,14}

Therefore, the sample size is calculated under the conservative assumption of

Clinical Investigational Plan

complication-free rate of 97%. Under this assumption, a sample size of 141 subjects will provide 90% power to reject the null hypothesis at a 2.5% significance level. The sample size was calculated using the exact binomial method in SAS® v9.4.

12.2.2 Sample size for primary efficacy endpoint #1 (Change in capture threshold for Durata or Optisure (RV) lead)

In the St. Jude Medical Accent MRI pacemaker IDE study, the results of which were submitted in PMA 60067410/A, the proportion of leads with an increase in threshold ≤ 0.5 volts from pre-MRI scan testing to 1-Month after the MRI scan was 100%.^{1,2}. Therefore, the sample size is calculated under the conservative assumption of 98% for the endpoint. Under this assumption, a sample size of 85 subjects will provide 80% power to reject the null hypothesis at a 2.5% significance level. The sample size was calculated using the exact binomial method in SAS® v9.4.

12.2.3 Sample size for primary efficacy endpoint #2 (Change in sensing threshold in Durata or Optisure (RV) lead)

In the St. Jude Medical Accent MRI pacemaker IDE study, the results of which were submitted in PMA 60067410/A, the proportion of leads with ‘ventricular sensing amplitude decrease of $\leq 50\%$ from pre-MRI scan testing to 1-Month after the MRI scan,’ was approximately 97%. Therefore, the sample size is calculated under the conservative assumption of 95% success rate for the ventricular sensing threshold endpoint. Under this assumption, a sample size of 118 subjects will provide 80% power to reject the null hypothesis at a 2.5% significance level. The sample size was calculated using the exact binomial method in SAS® v9.4.

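### The symptom instruction relied on to capture every MRI-caused event stops at scanner exit, while the safety endpoint runs to 1 month and the CEC sees late non-fatal events only if the site calls them device-related

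*Combined protocol and SAP*

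**What the plan says.** Section 8.1.4 directs sites to 6.5.2.2 as the means of capturing all ADEs and SADEs caused by or related to the scan. It describes clotting, pulmonary embolism and pocket heating this way: "These events are likely to be associated with symptoms occurring during or immediately following the MRI scan".

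Section 6.5.2.2 has staff tell the subject, before the scan, to report chest pain, breathlessness or discomfort at the pocket "that he/she experiences while being scanned or immediately after exiting the scanner". Its work-up for suspected clotting, embolism or heating is tied to the same period.

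The endpoint in section 4.4.1 covers a longer period: freedom from MRI scan-related complications "from MRI scan to 1 month post-MRI scan testing is greater than 90" per cent. Table 1 in the Synopsis places the closing visit at "30 days after MRI scan (- 7/+14 days"). Section 8.1.6 also extends MRI-relatedness through that visit and rests it on CEC adjudication. Table 2 in section 3.3 lists "Lead heating resulting in thrombus formation or embolism" among the potential MRI-related events, with no time limit.

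**The concern.** The procedure named as capturing everything asks about these symptoms only in the first moments of a window that lasts 23 to 44 days. Thrombus, embolism and tissue damage in the pocket can declare themselves later. After scanner exit, the protocol text does not ask for them by name.

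There is also a filter before adjudication. Under 8.1.2 an event is an ADE only if it is related to the device, and under 14.1 the CEC reviews ADEs and all deaths. Suppose a site judges a non-fatal embolism on day 10 to be unrelated. It is then not an ADE, and nothing in the text sends it to the committee that decides relatedness for the endpoint. The timing sentence in 8.1.4 could be read as support for that judgement.

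The trial is single-arm with a fixed performance goal, so a complication lost in this way is counted as a success. The error runs in one direction only, towards passing.

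**Working it through.** **1. The passages side by side**

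| Element | Period or route | Section |
|---|---|---|
| Named symptom instruction to the subject | Scan and immediately after exit | 6.5.2.2 |
| Trigger for the clotting, embolism and heating work-up | Scan and immediately after | 6.5.2.2 |
| Safety endpoint; MRI-related complication | Scan to 1-month visit, day 30 − 7 = 23 to 30 + 14 = 44 | 4.4.1, 8.1.6, Table 1 |
| General ADE/SADE evaluation | 1-month visit; unscheduled visits before it | 6.5.3.1, Tables 1 and 5 |
| Targeted prompt at 1 month | Significant rise in pacing threshold only | 6.5.2.2, 6.5.3.1 |
| Events reaching the CEC | ADEs and all deaths | 14.1, 8.3.1 |

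The unscheduled-visit route helps only in part. Section 6.9 defines such a visit as one prompted by an ADE, SADE or UADE, or by VT/VF collection. A subject treated elsewhere for an embolism need not generate one.

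Section 8.2.2 makes ADEs reportable even when they are not associated with the scan, but the event must still be an ADE. Section 8.2.1, read literally, makes any event non-reportable if it is unrelated to a procedure to remove, replace or reposition the lead or ICD. That conflicts with 8.2.2.

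**2. Reproducing the plan's sample size**

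Inputs from 12.1.1 and 12.2.1: null rate 90%; assumed "complication-free rate of 97"%; n = 141; power 90%. "The hypothesis will be tested at the 2.5% significance level", and "The null hypothesis will be rejected if the 97.5% lower confidence bound for p_S is greater than 90"%, using the exact Clopper-Pearson bound.

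- With 7 complications (134/141 free) the lower bound is 90.04%, which passes. With 8 it is 89.13%, which fails. The test therefore passes with at most 7.
- Exact type I error: P(X ≤ 7), X ~ Binomial(141, 0.10), = 0.0242.
- Exact power at 97%: P(X ≤ 7), X ~ Binomial(141, 0.03), = 0.937.
- At n = 140 power is 0.871. From 141 upwards it stays at or above 90%, so the stated 141 reproduces.

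**3. What missed complications would do**

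If k complications are not counted, the test passes when the true count is at most 7 + k. With n = 141 and a true complication rate of 10% (141 × 0.10 = 14.1 expected):

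| Missed (k) | Formula | Chance of passing |
|---|---|---|
| 0 | P(X ≤ 7) | 0.0242 |
| 1 | P(X ≤ 8) | 0.0502 |
| 2 | P(X ≤ 9) | 0.0928 |

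Alternatively, let a fraction s of complications be captured, so that the observed rate is the true rate times s:

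| True complication rate | s = 100% | s = 90% | s = 75% | s = 50% |
|---|---|---|---|---|
| 10% | 0.024 | 0.055 | 0.163 | 0.591 |
| 3% | 0.937 | 0.962 | 0.985 | 0.999 |

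The documents give no capture rate. Both k and s are assumptions.

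**The case against.** The strongest reply is that late events are in fact sought. A general ADE/SADE evaluation is required at the 1-month visit, at earlier unscheduled visits, at system revisions and at induction visits. Section 8.2 collects all ADEs, serious or not, once the MRI Settings are programmed. This stands. A reader might infer from 6.5.2.2 that delayed events are not solicited at all, and the documents contradict that. What is absent is a question that names the symptoms.

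A reader might also infer that delayed events are likely to be called unrelated. The text does not establish this. The sentence in 8.1.4 is descriptive and sets no time cut-off, 8.1.6 extends relatedness to the 1-month visit, and Table 2 lists embolism without a time limit. How sites would attribute such events is inference. The filter in 8.1.2 and 14.1 is in the text, although it applies to every type of event and is not created by 8.1.4.

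The endpoint is also narrow. Under 8.1.5 only an SADE that needed an invasive intervention or caused death counts. Such events are unlikely to go unmentioned at a required visit, and all deaths reach the CEC. This limits the likely number lost, and makes non-attribution a more plausible route than non-detection.

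Finally, the consent pages were removed from the material reviewed, and the CRFs and CEC charter are kept separately. It cannot be said that subjects are never told to call about later symptoms, or that the Follow Up CRF has no symptom items. The point concerns the protocol text only.

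**Conclusion.** The point holds as a gap in ascertainment and routing that is cheap to close. Section 8.1.4 claims more for 6.5.2.2 than its scan-time instruction can deliver. A late non-fatal clotting, embolic or pocket event that a site calls unrelated may not reach the body that decides relatedness. Any loss of a qualifying complication favours a pass.

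The size is unknown. The 5.0% and 9.3% figures assume a true complication-free rate of exactly 90% and one or two complications missed. They are illustrations and should not be read as the trial's type I error. Under the plan's own 97% assumption, the chance of passing is already 93.7%, so under-capture could add at most 1 − 0.937 = 0.063. A missed event changes the result only when the true count is just above the limit: 8 if one is missed, 8 or 9 if two are. The sample size and stated power are unaffected.

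**What to change.** 1. In 6.5.2.2 and 8.1.4, extend the subject's reporting instruction for chest pain, breathlessness and pocket symptoms from the scan through the 1 Month Post Scan visit. In 6.5.3.1, ask about each by name.
2. Qualify the timing sentence in 8.1.4 so that late onset alone is not a reason to call an event unrelated.
3. In 8.2.2 and 14.1, require every clotting, embolic or device-pocket event from the scan to the 1-month visit to be reported and sent to the CEC regardless of the site's attribution. Reconcile the non-reportable bullet in 8.2.1 with 8.2.2.

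The cost is wording in these sections, a few yes/no items on the Follow Up CRF if they are not already there, and a few extra events for the CEC, most of them probably unrelated. No visit or procedure is added, and no diagnostic or treatment rule changes.
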